2.1 Data analysis general information

The data will be analyzed by Novartis and/or by the designated CRO (clinical research organization). It is planned that the data from all centers that participate in this protocol will be used for analysis. Analysis datasets and statistical outputs will be produced using the most recent SAS® Version 9.4 (SAS Institute Inc., Cary, NC, USA), and stored in Novartis global programming & statistical environment (GPS).

Summary statistics for continuous variables will include number of patients (n), mean, standard deviation, minimum, lower quartile, median, upper quartile, maximum. Summary statistics for discrete variables will be presented in the number and percent of patients in each category. Summary statistics will also be presented graphically wherever applicable.

The two-sided p-values and confidence interval (CI) will be presented.

Data analyses will be presented by treatment group for both period I and period II separately. Efficacy and safety data for the placebo-controlled period I will be presented by the following 2 treatment groups of A and B whereas for period II the data will be presented for 5 treatment groups A1, A2, A3, B1 and B2.

The analysis will be conducted on all patients' data at the time the trial ends (Week 24).

Comparative efficacy data

Comparative efficacy analyses (i.e. inferential efficacy comparisons with placebo) will focus on the Treatment Period 1, when active drug and the placebo are given in a manner suitable for making comparisons (i.e., first 8 weeks of treatment). Comparative efficacy will be performed based on the FAS-TP1 population using the randomized treatment for Treatment Period 1. After week 8 till week 24, the efficacy endpoints will be summarized descriptively or otherwise specified using inferential analysis, on the FAS population using the randomized/re-assigned treatment for Treatment Period 2.

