## 1.2 Purpose

The purpose of the study is to evaluate the efficacy and safety of secukinumab 150 mg compared to placebo in the early management (Baseline to Week 8) of spinal pain, disease activity, fatigue and predictability of disease flares in patients with axSpA who have an inadequate response to prior NSAIDs. This study will also assess the efficacy and safety of secukinumab 300 mg compared to secukinumab 150 mg from Week 8 to Week 24 in order to assess the potential additional benefits of dose escalation in patients with axSpA.

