Proportion of patients achieving a satisfactory Patient Acceptable Symptom State (PASS) at Week 1, 2, 3, 4 and 8 with secukinumab 150 mg compared to placebo.	Proportion of patients achieving a satisfactory PASS at Week 1, 2, 3, 4 and 8 in Group A compared to Group B.

Proportion of patients in each of treatment arm achieving a satisfactory PASS at Week 12, Week 20 and Week 24.	Proportion of patients achieving a satisfactory PASS at Week 12, Week 20 and Week 24 in Arm A1, Arm A2 vs Arm A3, and Arm B1 vs Arm B2.
Spinal pain NRS score according to previous exposure to tumor necrosis factor (TNF) inhibitors at Week 1, 2, 3, 4, 8, 12 and 24	Proportion of patients achieving a spinal pain score < 4 for TNF-naïve patients compared to TNF α -IR patients at Week 1, 2,3, 4, 8, 12 and Week 24
Proportion of patients who responded to secukinumab 150 mg at Week 8 (i.e. spinal pain score < 4 on a 0-10 NRS) maintaining a response at Week 24.	Proportion of patients with spinal pain score < 4 on a 0-10 NRS at Week 8 maintaining a spinal pain score < 4 at Week 24.
Proportion of patients achieving an improvement in ASAS health index with secukinumab 150 mg compared to placebo at Week 8.	Proportion of patients achieving an improvement in ASAS health index with secukinumab 150 mg compared to placebo at Week 8.
Proportion of patients achieving an improvement in ASAS health index in each treatment arm at Week 24.	Proportion of patients achieving an improvement in ASAS health index in each treatment arm at Week 24.
ASAS health index at Week 8 and Week 24.	Mean ASAS health index score in each treatment arm at Week 8 and Week 24
Change from baseline in total spinal pain NRS score at all time points.	Total spinal pain NRS score in each treatment arm at all time points.
Change from baseline in total BASDAI score at all time points.	Total BASDAI score in each treatment arm at all time points.
ASDAS-CRP at Week 8 and Week 24.	Mean ASDAS-CRP in each treatment arm at Week 8 and Week 24.
[REDACTED]	
[REDACTED]	
Safety and tolerability of secukinumab 150 mg and 300 mg over the study period.	Safety and tolerability, as measured by frequency and severity of adverse events and changes in laboratory values of interest for secukinumab 150 mg and placebo (Baseline to Week 8) and for secukinumab 150 mg and 300 mg (Week 8 to Week 24).

2 Statistical methods

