2.8 Safety analyses

All the safety analysis will be performed on the Safety Sets for period I and period II separately and also for entire treatment period, where applicable. Summaries will be performed separately for period I (from baseline to Week 8) and period II (from dosing at Week 8 to Week 24).

The safety follow-up will be carried forward until 12 weeks after the last study treatment. The analyses of the follow-up period will be consolidated to summaries for treatment-emergent adverse events, and serious adverse events to Treatment Period 2.

Safety analyses will be performed on treatment received or actual treatment as described below:

The actual treatment or treatment received for summaries of safety data will differ to the treatment assigned at randomization only, if a subject received the wrong treatment during the entire study.

For those patients who received erroneously at least once, the wrong treatment (not the correct one at randomization) an additional AE listing will be prepared displaying which events occurred after the treatment errors and the relationship with study drug.

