2.14 Interim analysis

No interim analysis is planned for this study.

3 Sample size calculation

To assess the assumed effect size at Week 8, a 43.6% response rate (spinal pain NRS < 4) is assumed for the secukinumab 150 mg group. This number is derived as an average of the response rates observed in the CAIN457F2320 and CAIN457F2310 studies ([Baeten et al 2015](#)). For the placebo group, a response rate at Week 8 of 23.5% (NRS < 4) was selected as assessed in the CAIN457F2320 study. This intermediate scenario takes into consideration a certain likelihood of a relatively high placebo response also in line with data from the TNF α reference studies and the CAIN457F2305 study in addition to the slightly milder course of the disease in the studied population ([Baeten et al 2015](#)).

Assuming conservatively a response rate of 23.5% in the placebo group and a response rate of 43.6% under secukinumab 150 mg, 332 patients in total (i.e. 249 patients in secukinumab 150 mg group and 83 patients in placebo group) would be needed under 3:1 (secukinumab: placebo) allocation to achieve 90% power on a (2-sided) 5% significance level. To compensate for drop-out patients or those with protocol deviations, a total of 352 patients (264 in secukinumab 150 mg group and 88 in the placebo group) should be recruited.

4 Change to protocol specified analyses

None.

5 Appendix

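### Exploratory safety, Weeks 8-24: the plan shows five arms but no contrast between the two randomised doses; adding A2+B1 v A3+B2, with Arm A1 kept apart, is a cheap improvement

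*SAP*

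**What the plan says.** Protocol 1.2 (Purpose) is comparative: "This study will also assess the efficacy and safety of secukinumab 300 mg compared to secukinumab 150 mg from Week 8 to Week 24". The matching safety endpoint, the last of the exploratory objectives in SAP Table 1.2-1, is described by dose: "for secukinumab 150 mg and 300 mg (Week 8 to Week 24".

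On presentation, SAP 2.1 states that "for period II the data will be presented for 5 treatment groups A1, A2, A3, B1 and B2", and SAP 2.4.1 lists the same five arms. SAP 2.8 adds that "All the safety analysis will be performed on the Safety Sets for period I and period II separately and also for entire treatment period". SAP 2.8.1 produces the adverse event tables by treatment without defining the columns further.

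SAP Table 1.2-1 names A2 against A3 and B1 against B2 as comparisons, but only for efficacy endpoints. No section combines A2 with B1 or A3 with B2, pooled or stratified. SAP 1.1 makes clear that Group A non-responders and Group B patients are re-randomised to a dose at Week 8, while Group A responders are re-assigned to 150 mg (Arm A1).

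**The concern.** The Protocol announces a safety comparison of two doses, and the design randomises dose in two strata, but no planned output delivers that comparison. Each pair is small. Taken alone it leaves a wide interval on any dose difference, although the trial holds a larger randomised comparison.

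The second risk is how the gap gets filled. If a dose summary is assembled after unblinding, someone must decide whether A1 counts as 150 mg. A1 holds only responders and has no 300 mg counterpart, so including it compares unlike patients. That choice is best fixed in advance.

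Dose is a live safety question in the documents themselves. Protocol 3.7 discusses infection rates at 300 mg and 150 mg from other trials, and infections are an adverse event topic of special interest in SAP 2.8.1.1.

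**Working it through.** **The plan's own figure.** SAP section 3 and Protocol 9.8 size the primary comparison only. They take 43.6% responders on active treatment against 23.5% on placebo and arrive at "332 patients in total (i.e. 249 patients in secukinumab 150 mg group and 83 patients in placebo group". The Fleiss formula for two proportions with continuity correction, two-sided 5%, 90% power, 3:1, gives 83 on placebo and 4 x 83 = 332 in total, an exact match. Without the correction it gives 77 and 308. No size or precision is stated for the Week 8-24 dose comparison, so that has to be derived.

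**Inputs**
- Recruited: 264 in Group A and 88 in Group B (SAP section 3: "a total of 352 patients (264 in secukinumab 150 mg group and 88 in the placebo group) should be recruited").
- Group A response at Week 8: 43.6% (same section), so 56.4% non-responders.
- Re-randomisation ratio: assumed 1:1. It is not in the visible text, and the design figures are not shown there.
- Event rates: assumed, shown over a range. The documents give none for this purpose.

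**Expected arm sizes**
- A1: 264 x 0.436 = 115.1.
- A2 and A3: 264 x 0.564 / 2 = 74.4 each.
- B1 and B2: 88 / 2 = 44 each.
- Combined doses: 74.4 + 44 = 118.4 each.
- The planned allowance for loss is 1 - 332/352 = 5.7%. Applied here it leaves 118.4 x 332/352 = 111.7 per dose.

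**Precision.** With event rate p in both arms and n per arm, the 95% half-width of the risk difference is 1.96 x sqrt(2p(1-p)/n). With 1:1 allocation in each stratum and a common p, the stratified estimate has the same variance as n = 118.4.

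| Assumed rate | A2/A3 | B1/B2 | Combined, stratified |
|---|---|---|---|
| 5% | 7.0 | 9.1 | 5.6 |
| 10% | 9.6 | 12.5 | 7.6 |
| 30% | 14.7 | 19.1 | 11.7 |
| 40% | 15.7 | 20.5 | 12.5 |
| 50% | 16.1 | 20.9 | 12.7 |

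Half-widths are in percentage points. Example at 40%: 1.96 x sqrt(0.48/74.4) = 15.7; 1.96 x sqrt(0.48/44) = 20.5; 1.96 x sqrt(0.48/118.4) = 12.5.

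Relative width does not depend on p: sqrt(74.4/118.4) = 0.79 against A2/A3 and sqrt(44/118.4) = 0.61 against B1/B2, so 21% and 39% narrower. For Group A response between 30% and 55% the ratios run from 0.76 to 0.82 and from 0.57 to 0.65. A 2:1 re-randomisation in both strata leaves the ratios unchanged.

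**What including A1 could do.** Suppose no dose effect and illustrative rates of 30% in A1, 40% in A2 and A3, and 50% in B1 and B2.
- All 150 mg (A1+A2+B1): (115.1 x 0.30 + 74.4 x 0.40 + 44 x 0.50) / 233.5 = 37.0%.
- 300 mg (A3+B2): (74.4 x 0.40 + 44 x 0.50) / 118.4 = 43.7%.
- A2+B1: 43.7%, equal to A3+B2, as it should be.

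The 6.7-point gap in the first comparison comes entirely from A1.

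**Whether the entire-period tables fill the gap.** SAP 2.8.1 counts active time over the whole study. For A3 that includes the weeks on 150 mg before Week 8, and the columns are not defined by dose. The duration rules for exposure-adjusted rates cover Period 1 and the entire period, with none for Period 2 alone. These tables cannot yield the randomised contrast for Weeks 8-24.

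**The case against.** The case for leaving the plan alone has real substance.

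- A reader might infer that the safety endpoint is itself 150 mg versus 300 mg. It is not: SAP Table 1.2-1 joins the doses with 'and', and Protocol 9.6 has exploratory endpoints summarised descriptively. The comparative wording is in Protocol 1.2.
- A reader might infer that a planned safety comparison is being split into two weak ones. The documents do not support that. The pairs are efficacy comparisons, and no between-dose safety contrast is planned at all.
- A reader might infer that separate display serves no purpose. It does. A2/A3 are non-responders with five earlier doses of 150 mg, whereas B1/B2 receive their first secukinumab at Week 8. Protocol 3.3 poses escalation and a higher starting dose as distinct questions, and first-exposure reactions could differ.
- A reader might infer that doses are never shown together. That is firm for Period 2 only, because the entire-period columns are left open.
- Counts of patients with an event can be added across arms from the five columns, so the data are not lost. It is not certain that anyone would wrongly add A1.
- Intervals for every special-interest grouping would be excessive, since SAP 2.8.1.1 lists some fifteen infection groupings alone.

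All of this stands. It limits the point to reporting and narrows the remedy. It does not remove the mismatch between Protocol 1.2 and the planned output. Nor does later addition of columns replace deciding beforehand which arms belong in the contrast.

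**Conclusion.** This is a worthwhile, low-cost improvement to exploratory safety reporting. The Protocol states a dose comparison of safety for Weeks 8-24 and the SAP specifies no output for it. Combining the two randomised strata gives about 118 v 118 patients, or about 112 v 112 after the implied 5.7% loss, and an interval about 21% narrower than A2/A3 alone and 39% narrower than B1/B2 alone.

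The absolute sizes rest on 1:1 re-randomisation, 43.6% response in Group A and assumed event rates. The relative gain is stable over the response rates and ratios checked. Even combined, the interval is about ±12.5 points at a 40% event rate, so this describes a dose difference and will not settle a small one.

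**What to change.** In SAP 2.1 and 2.8:

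- Keep the five Period 2 columns. Add '150 mg randomised' (A2+B1) and '300 mg randomised' (A3+B2) for Weeks 8-24. Show Arm A1 separately, and state that its patients were re-assigned as responders and not randomised.
- Give the Mantel-Haenszel risk difference stratified by Period 1 group, with a two-sided 95% CI, for any AE, any SAE, AEs leading to discontinuation and the main special-interest topics (for example infections overall). Give counts only for sparse subgroups.
- Show the A2/A3 and B1/B2 differences beside the combined figure and label all of it exploratory.
- Define the treatment columns of the entire-period tables.
- State the Week 8 re-randomisation ratio in the text. Unstratified pooling is safe only if the ratio is the same in both strata.

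The cost is SAP wording, two table columns and a short set of estimates, with no change to conduct or data collection. The downside is that the combined figure averages non-responders already exposed to 150 mg with patients new to the drug, which is why the pairs stay visible.

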2.1.1 General definitions

Study treatment: Study treatment refers to:

Secukinumab 150 mg provided in 1 ml PFS or secukinumab placebo provided in 1 ml PFS.

Study treatment start and end date: Study treatment start date is defined as the first date, when a non-zero dose of study drug is administered and recorded on the Drug Administration Record (DAR) CRF page. Similarly, study drug end date is defined as the last date, when a non-zero dose of study drug is administered and recorded on the DAR CRF page of the core study.

Study day: Study day will be calculated as (event date – study drug start date + 1 day) for events that occurred on or after study drug start date (e.g., visit, lab samples, AEs). For events prior to study drug start date (e.g., time of diagnosis), study day will be negative and calculated as (event date – study drug start date). Note that study drug start date is study day 1 and the day before study drug start date is study day -1 (i.e. no study day 0).

Due to the study drug dosing schedule, one month will be considered as 28 days. However, for “time since event” data (e.g., medical history), one month will be considered as 365.25/12 days for events that occurred prior to study Day 1. Time from events prior to the start of study drug, e.g., time since diagnosis, is calculated as the difference between the start date of study drug and the date of prior event.

Note that, the first dose day is Day 1, and the day before the first dose day is counted as Day - 1 (not Day 0).

Baseline and post baseline: In general, a *baseline* value refers to the last measurement made prior to administration of the first dose of study treatment. A post-baseline value refers to a measurement taken after the first dose of study treatment.

Treatment Period: There are 2 treatment periods for this study defined as:

Treatment Period 1 is defined as an 8-week placebo-controlled, double-blind treatment period starting from baseline till Week 8. Assessments of Week 8 are included in TP1 whereas administration of study drug at week 8 will be a part of TP2. Week 8 is the last visit of TP1 for all assessments except drug intake.

Treatment Period 2 is a 16 week double-blinded, active treatment period starting from Week 8 till Week 24 for administration of study drug. Week 8 assessments are considered as the baseline values for assessments during TP2.

Lost to follow up: The patients whose study completion status is unclear because they fail to appear for study visits without stating an intention to withdraw.

On-treatment period: The period where the patients are exposed to the study treatment. For this study, the treatment phase consists of 24 weeks. For this study, the treatment phase consists of 8 weeks of on-treatment for period I (for treatment group A or group B) for secukinumab or placebo respectively, and 16 weeks of on-treatment for period II (for treatment group A1, A2, A3, B1 and B2) for secukinumab with 150 mg or 300 mg.

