Exploratory objectives	
 
Proportion of patients achieving a spinal pain score < 4 on a 0-10 NRS at Week 1, 2, 3 and 4 with secukinumab 150 mg compared to placebo.
 
Proportion of patients in each treatment arm achieving a spinal pain score < 4 on a 0-10 NRS at Week 24.
 
Proportion of patients in each treatment arm achieving a BASDAI score < 4 at Week 24.
 
Proportion of patients in each treatment arm achieving Ankylosing Spondylitis Disease Activity Score (ASDAS) score < 2.1 at Week 8 and Week 24.
 
Proportion of patients in each of treatment arm achieving ASDAS score < 1.3 at Week 8 and Week 24.
 
Mean change from Baseline in functional assessment of chronic illness therapy-fatigue (FACIT-Fatigue®) score in patients on secukinumab 150 mg compared to placebo at Week 8.
 
Mean change from Baseline in FACIT-Fatigue® score in each treatment arm at Week 24.
 
Proportion of patients in Arm A1 who have pain flares defined as NRS score > 6 at Week 12 or Week 24.
 
Proportion of patients achieving a satisfactory Patient Acceptable Symptom State (PASS) at Week 1, 2, 3, 4 and 8 with secukinumab 150 mg compared to placebo.
 
Proportion of patients in each treatment arm achieving a satisfactory PASS at Week 12, Week 20 and Week 24.
 
Spinal pain NRS score according to previous exposure to tumor necrosis factor (TNF) blockers at Week 1, 2, 3, 4, 8, 12 and 24.
 
Proportion of patients achieving a spinal pain score < 4 on a 0-10 NRS for TNF-naïve patients compared to TNF<math>\alpha</math>-inadequate responder (TNF<math>\alpha</math>-IR) patients at Week 8 and Week 24.
 
Proportion of patients who responded to secukinumab 150 mg at Week 8 (i.e. spinal pain score < 4 on a 0-10 NRS) maintaining a response at Week 24.
 
Proportion of patients achieving an improvement in Assessment of SpondyloArthritis International Society (ASAS) health index with secukinumab 150 mg compared to placebo at Week 8.
 
Proportion of patients achieving an improvement in ASAS health index in each treatment arm at Week 24.
 
ASAS health index at Week 8 and Week 24.
 
Change from baseline in total NRS score at all time points.
 
Change from baseline in total BASDAI score at all time points.
 
ASDAS-CRP at Week 8 and Week 24.
 
████████████████████
 
Safety and tolerability of secukinumab 150 mg and 300 mg over
 

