At Week 8, patients will enter Treatment Period 2 (Week 8 to Week 24). Patients randomized to Group A (secukinumab 150 mg) at Baseline will be assessed for the achievement of spinal pain NRS score and will be classified as responders (spinal pain NRS score < 4) or non-responders (spinal pain NRS score ≥ 4). Responders will be re-assigned to 1 treatment arm (Arm A1) to continue double-blind treatment with secukinumab 150 mg every 4 weeks from Week 8 to Week 24 (last dose administered at Week 20). Non-responders will be separately re-randomized to 1 of 2 arms to receive double-blind treatment with either secukinumab 150 mg or secukinumab 300 mg every 4 weeks starting at Week 8 up to Week 24 (last dose administered at Week 20).

Patients on secukinumab 150 mg who achieve spinal pain NRS score < 4 at Week 8 will be re-assigned to continue secukinumab 150 mg every 4 weeks (Arm A1)

- **Arm A1:** secukinumab 150 mg (1 x 1.0 mL) plus placebo (1 x 1.0 mL) administered at Week 8, 12, 16 and 20

Patients on secukinumab 150 mg who do not achieve spinal pain NRS score < 4 at Week 8 will be re-randomized to continue secukinumab 150 mg every 4 weeks (Arm A2) or to escalate to secukinumab 300 mg every 4 weeks (Arm A3):

[figure not shown]
- **Arm A2:** secukinumab 150 mg (1 x 1.0 mL) plus placebo (1 x 1.0 mL) administered at Week 8, 12, 16 and 20
- **Arm A3:** secukinumab 300 mg (2 x 1.0 mL) administered at Week 8, 12, 16, and 20

At Week 8, patients randomized to Group B (placebo) at Baseline will be re-randomized to either secukinumab 150 mg every 4 weeks (Arm B1) or secukinumab 300 mg every 4 weeks (Arm B2)

- **Arm B1:** secukinumab 150 mg (1 x 1.0 mL) plus placebo (1 x 1.0 mL) administered at Week 8, 12, 16 and 20
- **Arm B2:** secukinumab 300 mg (2 x 1.0 mL) administered at Week 8, 12, 16, and 20

During the study, patients will be required to self-administer secukinumab or placebo at all study visits and at home at Week 16.

On each treatment day during Treatment Period 2, two s.c. injections will be administered via PFSs either as 1 injection of secukinumab 150 mg and 1 injection of placebo, or 2 injections of secukinumab 150 mg. This is necessary to maintain the blind since secukinumab is supplied in 1.0 mL PFSs each containing 150 mg secukinumab, i.e. secukinumab 150 mg is supplied as 1 PFS and secukinumab 300 mg as 2 PFSs. Placebo to secukinumab will be supplied in 1.0 mL PFSs to match the active drug.

Figure 1-1 Study design

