2.11 Patient-reported outcomes

Variables related to health-related quality of life (HR-QoL) are described below. All HR-QoL variables will be evaluated based on the FAS-TP1 and FAS-TP2 population at (Baseline to Week 8) and (Week 8 to Week 24) respectively.

FACIT-Fatigue[®] score

- Change from baseline in FACIT-Fatigue[®] score for each treatment group at Week 8.
- Change from baseline in FACIT-Fatigue[®] score for each treatment group at Week 24.
- Change from Week 8 in FACIT-Fatigue[®] score for each treatment group at Week 24.

All FACIT scales are scored so that a high score is good.

To achieve this, we reverse response scores on negatively-phrased questions. The total score is then calculated as the sum of the un-weighted subscale scores.

Calculate the score only if at least 11 questions are answered.

Calculate the total score as mentioned in below table:

Item Number	Reverse Item?		Item Response	Item Score
1	4	-		=
2	4	-		=
3	4	-		=
4	4	-		=
5	4	-		=
6	4	-		=
7	0	+		=
8	0	+		=
9	4	-		=
10	4	-		=
11	4	-		=
12	4	-		=
13	4	-		=

Sum individual item scores: _____

Multiply by 13: _____

Divide by number of items answered: _____

Patient Accepted Symptoms State

- Proportion of patients in each treatment group with satisfactory PASS at Week 1, 2, 3, 4 and 8.
- Proportion of patients in each treatment group with satisfactory PASS at Week 12, 20 and 24.

ASAS Health Index

- Proportion of patients in each treatment group of achieving a minimal improvement (MCII) in ASAS health index at Week 8.
- Proportion of patients in each treatment group of achieving a minimal improvement (MCII) in ASAS health index at Week 24.

- Proportion of patients in each treatment group of achieving a significant improvement (SCI) in ASAS health index at Week 8.
- Proportion of patients in each treatment group of achieving a significant improvement (SCI) in ASAS health index at Week 24.
- Change from baseline in ASAS health index for each treatment group at Week 8 and Week 24.

Total Score calculation:

Total Score will be analyzed, if no more than 20% of data is missing. The total score is calculated as follows for respondents with one to a maximum of three missing responses

$$\text{Sumscore} = \{x/(N-m)\} * N$$

Where

x= Item summation score

N=Total no of items applicable (Items “I have lost interest in sex.” and “I have difficulty operating the pedals in my car” can be not applicable for few patients).

m=Number of missing Items

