- Proportion of patients in each treatment group with response in spinal pain score < 4 at Week 24.
- Proportion of patients in each treatment group with response in BASDAI score < 4 at Week 24.
- Proportion of patients in each treatment group with response in ASDAS score < 2.1 at Week 8 and Week 24.
- Proportion of patients in each treatment group with response in ASDAS score < 1.3 at Week 8 and Week 24.
- Proportion of patients in Arm 1 with spinal pain score > 6 at Week 12 or Week 24.
- Proportion of patients achieving a spinal pain score < 4 for TNF-naïve patients compared to TNF α -inadequate responder (TNF α -IR) patients at Week 8 and Week 24.
- Proportion of patients with response in spinal pain score < 4 to secukinumab 150 mg at Week 8 maintaining a response at Week 24. Only descriptive statistics will be presented for this endpoint.

The statistical significance of the above endpoints between groups will be analyzed by 95% CI of proportion. P-value will be added if there are enough number of patients available. The following continuous exploratory endpoints will also be summarized descriptively with number of patients (n), minimum, mean, standard deviation, median and maximum.

- Change from baseline in spinal pain score according to previous exposure to tumor necrosis factor (TNF) blockers at Week 1, 2, 3, 4, 8, 12 and 24.
- Change from baseline in total spinal pain score at all time points by each treatment group for each treatment period.
- Change from baseline in total BASDAI score at all time points by each treatment group for each treatment period.
- Change from baseline in ASDAS-CRP at Week 8 and Week 24.

If for a significant number of patients, the assignment to responder and / or non-responder status is incorrect, then a risk analysis may be performed.

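### SAP 2.1.1 makes Week 8 the baseline for Treatment Period 2, against the protocol and SAP 2.11, and so puts regression to the mean into within-arm pain changes for arms formed on the Week 8 score

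*SAP*

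**What the plan says.** **SAP, definition.** Section 2.1.1 first gives a general rule: a baseline value "refers to the last measurement made prior to administration of the first dose of study treatment". In the same section, under Treatment Period, it adds that "Week 8 assessments are considered as the baseline values for assessments during TP2". The first rule is worded as holding in general, so the second, which is specific to Period 2, would normally override it.

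**Protocol, objectives.** The exploratory objectives in the Protocol summary include "Change from baseline in total NRS score at all time points" and "Change from baseline in total BASDAI score at all time points", and change from Baseline in FACIT-Fatigue at Week 24. Protocol 9.5.2.2 and 9.5.2.3 ask for change from Baseline in laboratory data and vital signs at each visit. No second baseline is defined.

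**SAP, outputs.** Section 2.13 plans "Change from baseline in total BASDAI score at all time points by each treatment group for each treatment period", with a matching line for total spinal pain. It does not say which baseline applies in Period 2. Section 2.11 lists change from baseline at Week 24 for FACIT-Fatigue and, separately, "Change from Week 8 in FACIT-Fatigue" at Week 24. Section 4 reports no change to the protocol-specified analyses.

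**How the arms are formed.** In SAP 1.1, Group A patients with a Week 8 spinal pain score below 4 are assigned to Arm A1 without randomization. For those at 4 or above, "Non-responders will be separately re-randomized to 1 of 2 arms", A2 or A3. Under Protocol 6.4.1 the score is the average of two ratings, nocturnal and total back pain.

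**The concern.** There are two problems, and the second makes the first worth fixing.

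The reference for Period 2 change is not settled. The SAP sentence departs from the protocol without being declared, and it would make the two FACIT-Fatigue outputs at Week 24 identical. It also sits badly with two lines in SAP 2.13 that run as one series across both periods: spinal pain change by prior TNF exposure (Weeks 1 to 24) and ASDAS-CRP change (Weeks 8 and 24). Two programmers could produce different Week 24 tables from this text.

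The Week 8 pain score is also the variable that sorts Group A into A1 and A2/A3. Change measured from the selecting value carries regression to the mean, upwards in the arm selected for low scores and downwards in the arms selected for high ones. Protocol 3.5 wants Period 2 to show whether A1 sustains its response and to explore the two regimens descriptively. A reader of within-arm mean changes could take selection for loss of benefit in A1 or late benefit in A2/A3.

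For laboratory and vital-sign data the same sentence would make Group A's Period 2 reference a value already on active drug.

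**Working it through.** **Inputs.** Week 8 response rate on secukinumab 150 mg p = 0.436 and Group A size 264 (Protocol 9.8, SAP section 3). Cut at 4 (SAP 1.1). The common SD of the Week 8 and Week 24 scores and their correlation r are not in the documents. I assume SD 1.5 to 2.5 and r 0.5 to 0.8.

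**The plan's own figure.** The 43.6% comes from the sample size section, so I checked that first. For 23.5% v 43.6%, two-sided 5%, 90% power and 3:1 allocation, the two-proportion formula gives 77 on placebo (308 in total) without continuity correction and 83 (332 in total) with it. The stated 332 is reproduced. At 43.6%, about 264 × 0.436 = 115 patients enter A1 and 264 × 0.564 = 149 are divided between A2 and A3.

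**Artefact with Week 8 as reference.** Let the Week 8 and Week 24 scores be bivariate normal with the same mean μ and SD, so that nothing truly changes after Week 8. Then E[X24 − X8 | X8] = −(1 − r)(X8 − μ). With the cut at quantile p, c = Φ⁻¹(0.436) = −0.161 and φ(c) = 0.394:

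- A1: (1 − r) × SD × φ(c)/p, with φ(c)/p = 0.394/0.436 = 0.90.
- A2 and A3: −(1 − r) × SD × φ(c)/(1 − p), with φ(c)/(1 − p) = 0.394/0.564 = 0.70.

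| SD | r | A1 | A2 and A3 |
|---|---|---|---|
| 1.5 | 0.5 | +0.68 | −0.52 |
| 1.5 | 0.8 | +0.27 | −0.21 |
| 2.0 | 0.5 | +0.90 | −0.70 |
| 2.0 | 0.8 | +0.36 | −0.28 |
| 2.5 | 0.5 | +1.13 | −0.87 |
| 2.5 | 0.6 | +0.90 | −0.70 |
| 2.5 | 0.8 | +0.45 | −0.35 |

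Over all of Group A the two parts cancel: 0.436 × 0.90 − 0.564 × 0.70 = 0 up to rounding. A2 and A3 have the same expected artefact, so their difference is 0.

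**Simulation check.** Half-point scale bounded at 0 and 10, entry above 4, assumed Week 0 mean 6.5 before the entry cut, 43.6% responders at Week 8, 1:1 split of non-responders, no true change afterwards, five SD and r pairs in the range above.

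- From Week 8: +0.31 to +1.19 in A1 and −0.24 to −0.92 in A2/A3. A3 minus A2 was at most 0.011 in absolute size.
- From Week 0: −2.74 to −3.33 in A1 and −2.64 to −2.80 in A2/A3. The opposite-signed artefact has gone, but the arms still differ because they were selected.
- Responders at Week 24: 60% to 75% of A1 and 19% to 31% of A2/A3. These proportions use no baseline.

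**Other measures.** For a measure Y other than the selecting score, (1 − r) is replaced by ρ8 − ρ24, the correlations of Y at Weeks 8 and 24 with the Week 8 average score, and SD by that of Y. Since ρ8 is below 1, the artefact should be smaller in SD units. This covers BASDAI, ASDAS-CRP and the single pain items. It may also cover the total spinal pain line in SAP 2.13, because SAP 2.5.3 and 2.5.4 treat total pain as one of the two items averaged.

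**The case against.** The best defence is that Week 8 is a sensible reference for Period 2. It is the last value before re-randomization and, in Group B, the last before active drug. It suits A2 v A3 and B1 v B2, and it introduces no bias there. That stands, and it is why change from Week 8 should be kept as a labelled output. It does not explain why the rule departs from the protocol undeclared, or why SAP 2.11 treats the two references as distinct.

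It is also fair that the effect is confined to exploratory, descriptive summaries and that real further improvement could hide the A1 artefact.

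A reader might infer more than the documents support:

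- *That every change from baseline at Weeks 12, 20 and 24 is reset.* The SAP is inconsistent, not uniform: FACIT-Fatigue keeps both references. ASDAS-CRP cannot be computed at Weeks 12 or 20, because hsCRP and patient global assessment are not scheduled then (Protocol Table 6-1). The protocol lists ASDAS-CRP at Weeks 8 and 24, not its change.
- *That A1 will appear to lose response.* Maintained response and flare are proportions on fixed cut-offs (NRS below 4, NRS above 6). Regression to the mean in them comes from selection and would be the same under either baseline.
- *That the reset could create an apparent advantage of 300 mg over 150 mg.* A2 and A3 are randomized within non-responders, and B1 and B2 are not selected on pain.
- *That the Week 0 to 8 gain is lost.* Period 1 change is reported for Group A, and Table 1.2-1 and SAP 2.13 plan score levels by arm and time courses. What may be missing is change from Week 0 split by A1, A2 and A3.

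**Conclusion.** The concern holds in a limited form. SAP 2.1.1 conflicts with the protocol's change-from-baseline objectives and safety summaries, with SAP 2.11, and with the statement of no changes in section 4. If followed, and absent true change after Week 8, within-arm mean change in average spinal pain would show apparent worsening of about 0.3 to 1.1 points in A1 and apparent improvement of about 0.2 to 0.9 points in each of A2 and A3.

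The direction follows from the selection rule. The size rests on approximate normality, the planned 43.6% response rate, and assumed values of SD and r.

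The primary and secondary analyses are at Week 8, and the repeated-measures model covers visits 2 to 7 only (SAP 5.4.1), so none is touched. Nor are the proportions on fixed cut-offs (NRS below 4, NRS above 6, BASDAI below 4) or the randomized Period 2 contrasts. A Week 0 reference removes this artefact but does not make A1 comparable with A2/A3.

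**What to change.** - In SAP 2.1.1, define Baseline as the last value before the first dose at Week 0 for all change-from-baseline outputs in both periods, including laboratory and vital-sign data. Delete the Week 8 sentence or restrict it to named outputs.
- Show change from Week 8 only as a separately labelled supplement, as SAP 2.11 already does for FACIT-Fatigue, with a note that A1, A2 and A3 were selected on the Week 8 score.
- State that dose comparisons in Period 2 are A2 v A3 and B1 v B2, and that within-arm changes in A1, A2 and A3 should not be set against each other.
- Record any Week 8 reference that is kept in SAP section 4.

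The cost is SAP wording, a baseline flag in the analysis datasets and at most a second set of descriptive tables. No data collection changes.
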